#### 5.4. Dose-Limiting Toxicity Criteria for the Dose Escalation Portion of the Study

Dose-limiting toxicity is defined as any of the following treatment-emergent adverse events that occurs during the 21-day Cycle 1 and that are judged by the Investigator as related to TTI-621 or the combination of TTI-621 and doxorubicin. Adverse events that are in the opinion of the Investigator attributable exclusively to intravenous infusion of doxorubicin or any doxorubicin prophylaxis medication will not be considered a dose-limiting toxicity.

CCI

CCI

Infusion-related reactions with TTI-621 are not unexpected and prophylaxis guidelines are provided in [Section 5.2.1.2](#) to mitigate their occurrence and/or severity. While the Investigator may decrease the duration of TTI-621 infusion and/or may decrease or eliminate the steroid component of TTI-621 prophylaxis in a patient who has not experienced infusion-related reaction, caution is urged with respect to implementing both changes simultaneously and a stepwise approach is recommended.

In the event that one patient in a cohort of three patients experiences a dose-limiting toxicity, the cohort will be expanded to a total of six patients. If at least two patients within a dose cohort experience a dose-limiting toxicity during the dose-limiting toxicity period, the conclusion may be drawn that the maximum tolerated dose of TTI-621 in combination with 75 mg/m^2 doxorubicin has been exceeded; any further dose escalation, de-escalation or cohort expansion will be decided in consultation between Investigators, the Sponsor Medical Monitor and the Sponsor after consideration of the particular patients and adverse events experienced, as well as all available safety and pharmacokinetic data of all cohorts.

**6. STUDY POPULATION****6.1. Number of Patients**

Up to approximately 80 patients are anticipated to participate in the study, with up to 18 in the dose escalation portion of the study and 31 in each of two expansion cohorts. Based on patient outcomes in the dose expansion portion of the study, additional patients may be added to further explore response and/or tolerability of study treatment at one or more dose levels of TTI-621.

**6.2. Inclusion Criteria**

Patients must meet all the following criteria to be enrolled in the study:

***General***

1. Written informed consent obtained prior to performing any study-specific procedure, including screening procedures
2. Men and women  $\geq$  18 years of age
3. ECOG Performance Status 0 or 1
4. Patients enrolled onto the dose expansion cohorts must agree to pre-treatment and on-treatment biopsies if deemed safe and feasible by the treating physician

***Disease Characteristics***

5. Histologically-confirmed high-grade soft tissue sarcoma that is metastatic or locally advanced and not amenable to curative treatment with surgery or radiation
  - In the dose escalation portion of the study, indications will be limited to high-grade leiomyosarcoma, undifferentiated pleomorphic sarcoma, myxofibrosarcoma, dedifferentiated liposarcoma, angiosarcoma and epithelioid sarcoma
  - In the expansion portion of the study, enrollment will be restricted to high-grade leiomyosarcoma that is histologically-confirmed at a central laboratory. The patient may be enrolled based on a current or most recent pathology report that provides sufficient detail to support derivation of the histologic interpretation but a pre-treatment tissue specimen must be made available for confirmation during screening or within the first cycle of treatment
6. Objective evidence of disease progression unless disease is newly-diagnosed
7. Measurable disease per RECIST v1.1 (expansion cohorts); target lesions must not be chosen from a previously-irradiated field unless there has been radiographically and/or pathologically documented tumor progression in that lesion prior to enrollment

***Organ Function***

Adequate organ and hematologic function as defined below:

8. Serum aspartate aminotransferase (AST) and alanine aminotransferase (ALT)  $\leq$  3 x ULN;  $\leq$  5 x ULN in the presence of liver metastasis
9. Serum bilirubin (total)  $\leq$  1.5 x ULN ( $\leq$  2 x ULN if hyperbilirubinemia is due to Gilbert's syndrome)
10. Serum creatinine  $\leq$  1.5 x ULN OR creatinine clearance/estimated glomerular filtration rate (eGFR)  $\geq$  40 mL/min/1.73 m^2 if serum creatinine is  $>$  1.5 x ULN

11. Hemoglobin  $\geq$  9 g/dL; packed RBC transfusions are not allowed in the week preceding screening evaluation
12. ANC  $\geq 1.5 \times 10^9/L$
13. Platelet count  $\geq 100 \times 10^9/L$
14. INR  $\leq 1.5 \times$  ULN ( $\leq 2.5 \times$  ULN if on anti-coagulants) and PTT  $\leq$  5 seconds above the ULN unless receiving anti-coagulation therapy; patients on full-dose anti-coagulation must be on a stable dose of oral anti-coagulant or low molecular weight heparin, have therapeutic INR, no active bleeding (defined as within 14 days prior to first dose of study medication) and no pathological condition that carries a high risk of bleeding (e.g., tumor involving major vessels or known varices)
15. LVEF determined by echocardiogram or multigated acquisition scan  $> 50\%$

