Inclusion Criteria	
General
 
 
1. Written informed consent obtained prior to performing any study-specific procedure, including screening procedures
 
2. Men and women <math>\geq</math> 18 years of age
 
3. ECOG Performance Status 0 or 1
 
4. Patients enrolled onto the dose expansion cohorts must agree to pre-treatment and on-treatment biopsies if deemed safe and feasible by the treating physician
 
 
Disease Characteristics
 
 
5. Histologically-confirmed high-grade soft tissue sarcoma that is metastatic or locally advanced and not amenable to curative treatment with surgery or radiation 
 
• In the dose escalation portion of the study, indications will be limited to high-grade leiomyosarcoma, undifferentiated pleomorphic sarcoma, myxofibrosarcoma, dedifferentiated liposarcoma, angiosarcoma and epithelioid sarcoma
 
• In the expansion portion of the study, enrollment will be restricted to high-grade leiomyosarcoma that is histologically-confirmed at a central laboratory. The patient may be enrolled based on a current or most recent pathology report that provides sufficient detail to support derivation of the histologic interpretation but a pre-treatment tissue specimen must be made available for confirmation during screening or within the first cycle of treatment
 
 
 
6. Objective evidence of disease progression unless disease is newly-diagnosed
 
7. Measurable disease per RECIST v1.1 (expansion cohorts); target lesions must not be chosen from a previously-irradiated field unless there has been radiographically and/or pathologically documented tumor progression in that lesion prior to enrollment.
 
 
Organ Function
 
Adequate organ and hematologic function as defined below:
 
 
8. Serum AST and ALT <math>\leq</math> 3 <math>\times</math> upper limit of normal (ULN); <math>\leq</math> 5 <math>\times</math> ULN in the presence of liver metastasis
 
9. Serum bilirubin (total) <math>\leq</math> 1.5 <math>\times</math> ULN (<math>\leq</math> 2 <math>\times</math> ULN if hyperbilirubinemia is due to Gilbert's syndrome)
 
10. Serum creatinine <math>\leq</math> 1.5 <math>\times</math> ULN OR creatinine clearance/estimated glomerular filtration rate (eGFR) <math>\geq</math> 40 mL/min/1.73 m^2 if serum creatinine is <math>></math> 1.5 <math>\times</math> ULN
 

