Statistical Considerations	
Based on a standard 3+3 design, up to approximately six patients may be enrolled in each dose level cohort evaluated during the dose escalation portion of the study; a minimum of nine and a maximum of 18 patients who complete the safety review period is anticipated.
 
The sample size for the dose level expansion cohorts is selected to obtain a reasonable estimate of clinical benefit, defined for this study as response rate defined by RECIST v1.1 criteria, to be used for planning future studies. A Simon two-stage design will be used for each dose cohort; in the Simon two-stage design and assuming a baseline overall response rate of 10% with doxorubicin monotherapy and an alternative of 25%, a power of 90% and one-sided Type 1 error set at 0.20, each dose level cohort will require 18 patients enrolled and evaluable for response in Stage 1. With at least two clinical responses, an additional 13 patients will be enrolled in Stage 2. The combination will be considered worthy of further study if at least five clinical responses observed in either 31-patient cohort.

Dose Delays, Dose Modifications, Guidelines for Treatment Discontinuation and Study Withdrawal	
Patients who enter the study with symptoms or laboratory values equivalent to NCI CTCAE Grade 1 or Grade 2 should not have dose reductions related to the persistence or mild worsening of those symptoms or laboratory values.
 
Dose reductions may be warranted if worsening of symptoms or laboratory values is clinically significant in the opinion of the Investigator and in the case of unacceptable treatment-related adverse events. Recognizing that it may be difficult to make attribution to one agent or the other in the combination regimen and in collaboration with the Sponsor Medical Monitor, best efforts should be made to consider the underlying reason for the worsening of symptoms or development of a treatment-related adverse event so that dosing of the appropriate study drug can be modified.
 
Except in the case of proteinuria, asymptomatic laboratory abnormalities should not result in dose interruptions, modifications, or discontinuation of study therapy unless determined by the Investigator to be clinically significant or life-threatening.

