**9.2.2. TTI-621 Re-Treatment Guidelines (Initiation of New Cycles of Treatment)**

The parameters described in [Table 9](#) should be met for initiation of a new cycle of treatment with TTI-621. Guidelines for intra-cycle dosing, dosing delays and dosing modifications in response to specific treatment-emergent adverse events are provided in Tables 12, 13, 14, 15, 21, 22 and 23.

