**Table 9. Requirements for Initiation of a New Cycle with TTI-621**

Parameter	Criterion
ANC	$\geq 1.0 \times 10^9/L$
Platelet Count	$\geq 75 \times 10^9/L$
Bilirubin	$\leq 1.5 \times ULN$
AST, ALT	$\leq 3 \times ULN$ ( $< 5 \times ULN$ if liver metastases)
Treatment-Related Adverse Event	NCI CTCAE Grade $< 2$ or baseline level (except for alopecia)

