**9.3. Management of Adverse Events Associated with Doxorubicin****9.3.1. Doxorubicin Treatment Interruptions**

Treatment with doxorubicin may be temporarily suspended for up to 42 days to allow for resolution of adverse events. Dose interruptions for reason(s) other than toxicity and re-treatment may be allowed in accordance with standard of care if the patient is receiving clinical benefit and after discussion with the Sponsor Medical Monitor. In general, if an interruption of more than 42 days is required due to adverse events, doxorubicin will be permanently discontinued; however, if in the judgment of the Investigator, the patient is likely to derive clinical benefit from doxorubicin after a hold of more than 42 days, study drug may be re-started with approval of the Sponsor Medical Monitor. Longer interruptions may be

acceptable on a patient-by-patient basis at the discretion of the Investigator after discussion the Sponsor Medical Monitor.

### 9.3.2. Doxorubicin Re-Treatment Guidelines for Day 1

The laboratory parameters described in [Table 16](#) should be met for re-treatment with doxorubicin.

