**Table 16. Requirements for Re-Treatment with Doxorubicin on Day 1 (Cycle 2 through Cycle 6)**

Parameter	Criterion
Platelets	$\geq 75 \times 10^9/L$
ANC	$\geq 1 \times 10^9/L$
Organ toxicity or other treatment-related adverse event	Grade $\leq 2$
Bilirubin	$\leq 1.5 \times ULN$
AST, ALT	$\leq 3 \times ULN$ ( $< 5 \times ULN$ if liver metastases)

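### Criterion 9 admits Gilbert's patients with bilirubin above 1.5 and up to 2 x ULN, but Tables 9 and 16 require 1.5 x ULN or less, so at an unchanged value they miss both re-treatment limits at Cycle 2

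*Protocol*

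**What the plan says.** **Entry.** Protocol Section 6.2, criterion 9, limits total bilirubin to 1.5 x ULN, with a higher limit of "2 x ULN if hyperbilirubinemia is due to Gilbert's syndrome". The Synopsis repeats the exception ("ULN if hyperbilirubinemia is due to Gilbert's syndrome").

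**TTI-621.** Section 9.2.2 says that the Table 9 parameters "should be met for initiation of a new cycle of treatment with TTI-621". The table is titled "Requirements for Initiation of a New Cycle with TTI-621", and its bilirubin row reads 1.5 x ULN or less.

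**Doxorubicin.** Section 9.3.2 says that the Table 16 laboratory parameters "should be met for re-treatment with doxorubicin". Its bilirubin row also reads 1.5 x ULN or less, and its title covers Day 1 of Cycles 2 to 6.

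Neither bilirubin row mentions Gilbert's syndrome or a baseline value. Table 9 does allow a return to baseline, but only in its separate row for treatment-related adverse events.

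**General rules.** The Synopsis (dose delays and modifications) says that, apart from proteinuria, "asymptomatic laboratory abnormalities should not result in dose interruptions, modifications, or discontinuation of study therapy" unless the Investigator finds them clinically significant or life-threatening. It also says that patients who enter with Grade 1 or 2 values "should not have dose reductions related to the persistence or mild worsening of those symptoms or laboratory values".

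**The concern.** The sponsor accepts a bilirubin value at screening and then, three weeks later, lists the same value as a reason not to start the next cycle of either drug. The higher entry limit exists only for patients above 1.5 x ULN, and those are exactly the patients whom the two tables exclude from re-treatment.

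At stake is consistent handling of an individual patient. Someone enrolled under the exception would receive one cycle, after which the site must decide whether the tables or the Synopsis text governs. Sections 3.7.2 and 6.7 say that six doxorubicin cycles are intended because fewer give less benefit, so a hold at Cycle 2 runs against the plan's own aim. In an expansion cohort, a stop before two cycles and a scan would also raise the question of whether the patient is counted or replaced. Protocol Section 12.2 makes that depend on the reason for withdrawal, while SAP Section 8.2 keeps every treated patient in the response-rate denominator.

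**Working it through.** **1. Do the two sets of values overlap?** Let b be total bilirubin as a multiple of ULN.

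- Needs the exception in criterion 9: 1.5 < b ≤ 2.0.
- Meets Table 9: b ≤ 1.5.
- Meets Table 16: b ≤ 1.5.

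No value satisfies the first line and either of the others. On a grid of 0.01 x ULN, 0 of 50 values in the window meet the limits. With the allowance written into both rows, 50 of 50 would. To start Cycle 2 under the present tables, a patient at the top of the window needs a fall of (2.0 − 1.5)/2.0 = 25%.

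**2. How are the neighbouring rows treated?**

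| Parameter | Entry (Section 6.2) | Tables 9 and 16 |
|---|---|---|
| ANC, x 10^9/L | 1.5 or more | 1.0 or more (looser) |
| Platelets, x 10^9/L | 100 or more | 75 or more (looser) |
| AST/ALT, liver metastases | up to 5 x ULN | below 5 x ULN (exception carried over) |
| Bilirubin, Gilbert's | up to 2 x ULN | 1.5 x ULN or less (exception not carried over) |

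**3. Treatment received by Cycle 2 Day 1.** Doxorubicin: 75 of 6 x 75 = 450 mg/m², or 16.7%. TTI-621: 2 of 6 x 2 = 12 combination-phase infusions, also 16.7%.

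**4. Effect on the two-stage design.** The plan enrols 18 then 13 patients, continues with at least 2 responses and is positive with at least 5. With X1 the Stage 1 responses and X2 the Stage 2 responses,

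P(positive) = Σ over x ≥ 2 of P(X1 = x) · P(X2 ≥ 5 − x).

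The design as written gives 0.902 at a 25% response rate and 0.182 at 10%, in line with the stated 90% power and 0.20 type 1 error. Now suppose that one Stage 1 patient is stopped, counted and unable to respond (17 then 13 at risk, same cut-offs):

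| True response rate | As designed | One such patient | Change |
|---|---|---|---|
| 25% | 0.902 | 0.883 | −0.019 |
| 10% | 0.182 | 0.164 | −0.018 |

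This applies to Cohort A only. SAP Section 4.3.2 closed Cohort B after its 18 Stage 1 patients and says that the two-stage design does not apply to Cohort C.

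**5. Does Table 18 touch the same patients?** It halves doxorubicin at bilirubin 1.5 to 3.0 mg/dL, with no Gilbert's allowance. The documents give no ULN. Assuming 1.0 to 1.3 mg/dL, the window runs from 1.5 x 1.0 = 1.5 to 2.0 x 1.3 = 2.6 mg/dL, inside that band. The halved dose would be 37.5 mg/m².

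**The case against.** The strongest reply is that the protocol leaves room to dose.

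- Sections 9.2.2 and 9.3.2 are headed as guidelines, and their parameters should, not must, be met.
- A stable, asymptomatic value accepted at entry fits the Synopsis statement that such abnormalities should not interrupt treatment.
- Section 9.2.1 lets TTI-621 restart after discussion with the Sponsor Medical Monitor. Section 9.3.1 has a similar consultation route for doxorubicin interruptions unrelated to toxicity.

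This stands. A reader might infer that an eligible patient cannot be re-treated at all, and the documents do not support that. What they lack is a rule of precedence. The Synopsis sentence is generic: read as overriding the tables, it would also loosen their ANC, platelet and transaminase limits. The non-toxicity routes in 9.2.1 and 9.3.1 ask that the patient be receiving clinical benefit, which is hard to show before the first scheduled scan at about six weeks. The other Synopsis sentence bars dose reductions, not holds.

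A second reply is that the stricter limit may be deliberate, since Table 18 shows that the sponsor adjusts doxorubicin for bilirubin. That cannot be excluded. The carried-over liver-metastasis exception suggests an oversight but does not prove one, so the fix below covers both intentions. Nor do the documents show whether a Gilbert's value would stay put between cycles.

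A third reply is that Table 18 would still halve the dose after Tables 9 and 16 are amended. This does not defeat the change: the Synopsis bars reductions for persisting Grade 1 or 2 entry values, and Table 18 is keyed to the worst toxicity of the prior cycle. But its bilirubin band has no Gilbert's carve-out, so a clarifying note is warranted.

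**Conclusion.** The inconsistency is in the text and does not depend on any estimate: every patient who needs the entry exception misses both bilirubin limits at Cycle 2 if the value has not changed. Gilbert's patients who enter at or below 1.5 x ULN are not affected.

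The consequence is modest. Dosing remains possible through Investigator judgment or Medical Monitor discussion, so the defect is an unresolved conflict that sites could settle differently. The number affected is not in the documents and may be none.

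A reader might also infer a threat to the Simon design. The figures do not support that. A shift of about 0.02 in either direction needs three assumptions together (such a patient exists in Stage 1 of Cohort A, is stopped rather than dosed, and cannot respond). The question of how early stops are counted arises for any such patient and is not specific to Gilbert's syndrome. The Table 18 overlap rests on the assumed ULN of 1.0 to 1.3 mg/dL, and the Synopsis protection against dose reduction applies if the entry value counts as Grade 1 or 2; the protocol does not print the CTCAE bilirubin scale.

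**What to change.** In the bilirubin rows of Tables 9 and 16, write: *≤ 1.5 x ULN (≤ 2 x ULN for a patient enrolled under the Gilbert's exception of criterion 9)*. This reuses the sponsor's own entry limit and the format that both tables already use for liver metastases. A value above 2 x ULN would still hold both drugs, and a Gilbert's patient enrolled at or below 1.5 x ULN would still be held above 1.5.

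In the hepatic-impairment rows of Table 18, add a note that the reduction does not apply to a stable entry-level bilirubin due to Gilbert's syndrome, consistent with the Synopsis.

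If the sponsor does intend 1.5 x ULN for every cycle, delete the Gilbert's exception from criterion 9 in both the Synopsis and Section 6.2 for any further enrolment. That option does nothing for patients already enrolled.

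Cost: two table cells and one note, or one clause deleted in two places. Neither needs new assessments or extra patients.

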***Previous Therapy***

16. No more than 1 prior treatment regimen for advanced disease, which is limited to gemcitabine with docetaxel
17. Anthracycline-naïve; anthracycline in the neoadjuvant/adjuvant setting renders the patient ineligible for participation
18. Patients who were treated with a prior chemotherapy regimen must have been completed treatment at least three weeks before initiation of study treatment
19. All adverse events from prior treatment must be NCI CTCAE v5 Grade  $\leq 1$ , except alopecia and stable neuropathy, which must have resolved to Grade  $\leq 2$  or baseline
20. Radiotherapy, including palliative radiotherapy, completed at least two weeks prior to treatment; palliative radiation to non-target lesions while on study is allowed

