In the combination portion of the study, Cycle 1 through Cycle 6, doxorubicin will be administered after emesis prophylaxis at  $75 \text{ mg/m}^2$  on Day 1 of each 21-day Cycle. It is intended that each patient will receive six cycles of doxorubicin as fewer than six cycles provides less benefit to the patient compared to six or more cycles and guidelines for prophylaxis for prevention of doxorubicin-mediated dose-limiting neutropenia are provided in [Section 5.2.1](#). Doxorubicin is administered through a free-flowing intravenous catheter in a volume of 100 mL by infusion over less than 60 minutes; prophylaxis for emesis should be given prior to each infusion and the site may follow institutional guidelines for prophylaxis and infusion as long as they do not contradict this requirement. The rate of infusion should be decreased if erythematous streaking along the vein proximal to the site of infusion or facial flushing occur. As described in [Section 5.2.1.1](#), prophylaxis with dexrazoxane for cardiotoxicity will begin no later than with initiation of Cycle 5 when cumulative doxorubicin will have reached  $300 \text{ mg/m}^2$ . Because of the potential for cumulative cardiac toxicity, a maximum of six cycles of doxorubicin (18 weeks of treatment) is permitted as per standard of care.

In Cycle 1 through Cycle 6, TTI-621 will be administered by intravenous infusion over 120 minutes on Day 1 and Day 8 of each 21-day cycle. Patients will receive prophylaxis as described in [Section 5.2.1.2](#) on each day of TTI-621 infusion for prevention of possible infusion-related reactions. Beginning with Cycle 2, the infusion period may be reduced to 60 minutes at the investigator's discretion if the patient has not experienced infusion-related reaction. In any cycle in which doxorubicin and TTI-621 are administered on the same day, doxorubicin treatment will precede administration of TTI-621; TTI-621 prophylaxis may begin prior to initiation of doxorubicin administration at the Investigator's discretion.

For the purposes of safety decisions that guide cohort expansion and considerations of TTI-621 dose adjustment in the dose escalation portion of the study, the safety period will consist of the 21-day Cycle 1. Subjects will be considered evaluable for dose-limiting toxicity if they received doxorubicin on Day 1.

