## 5.2. Doses and Schedule of Administration of Investigational Agents

In Cycle 1 through Cycle 6, patients will receive TTI-621 and doxorubicin. Prophylaxis for known adverse events associated with each agent is required as described below in [Sections 5.2.1.1](#) and [5.2.1.2](#).

Doxorubicin is administered on Day 1 of each cycle. Doxorubicin treatment is limited to a maximum of six cycles to avoid development of cardiac toxicity. It is intended that each patient will receive six cycles of doxorubicin as fewer than six cycles provides less benefit to the patient compared to six or more cycles and guidelines for prophylaxis for prevention of doxorubicin-mediated dose-limiting neutropenia are provided in [Section 5.2.1](#).

In Cycle 1 through Cycle 6, TTI-621 will be administered on Day 1 after completion of the doxorubicin infusion and on Day 8. For clarity, doxorubicin is not administered on Day 8.

In Cycle 2 through Cycle 6, in the event that doxorubicin dosing is held due to an adverse event from which the investigator believes the patient will recover and continue treatment, TTI-621 treatment will also be held. The day on which doxorubicin is re-initiated will then be considered Day 1 of the cycle, and TTI-621 will also be administered as planned on the new Day 1 and subsequent Day 8. Initiation of subsequent cycles will be reset according to the new Day 1.

Beginning with Cycle 7, TTI-621 will be administered as monotherapy on Day 1 and Day 15 of 28-day cycles.

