### 9.3.3.6. Radiation Sensitization and Radiation Recall Related to Doxorubicin Administration

Doxorubicin can increase radiation-induced toxicity to the myocardium, mucosa, skin and liver. Radiation recall, including but not limited to cutaneous and pulmonary toxicity, can occur in patients who receive doxorubicin after prior radiation therapy. Patients should not receive radiation unless there is an urgent or emergent need.

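### For non-urgent palliative radiation to a non-target lesion during the doxorubicin cycles, inclusion criterion 20 says yes, Section 9.3.3.6 advises no, and nothing says which governs

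*Protocol*

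**What the plan says.** Criterion 20 appears in the same terms in the Synopsis and in Section 6.2, under Previous Therapy. Its first half requires earlier radiotherapy, palliative courses included, to have finished at least two weeks before treatment. Its second half covers the study itself: "palliative radiation to non-target lesions while on study is allowed". The only conditions are palliative intent and a non-target lesion.

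Section 9.3.3.6 belongs to the guidance on managing doxorubicin adverse events. It gives two reasons for caution. The first is sensitization: "Doxorubicin can increase radiation-induced toxicity to the myocardium, mucosa, skin and liver". The second is radiation recall, which "can occur in patients who receive doxorubicin after prior radiation therapy". It then advises: "Patients should not receive radiation unless there is an urgent or emergent need". It makes no exception for palliative intent or non-target lesions, and it names no cycles.

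On the length of the doxorubicin phase, Section 5.1 states that "a maximum of six cycles of doxorubicin (18 weeks of treatment) is permitted as per standard of care". Section 9.3.1 allows holds: "Treatment with doxorubicin may be temporarily suspended for up to 42 days to allow for resolution of adverse events", with longer holds possible after discussion with the medical monitor. When a dose is held, Section 5.2 adds: "Initiation of subsequent cycles will be reset according to the new Day 1".

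**The concern.** A site asking whether a patient may have palliative radiation on study will probably look first at the eligibility list, where the answer is an unqualified yes. The caution is in a subsection on doxorubicin toxicity that the eligibility list does not mention. A site relying on criterion 20 could schedule elective radiation between two doxorubicin doses. The patient would then be open to the sensitization that Section 9.3.3.6 describes and, when the next dose follows, to recall. A site that starts from Section 9.3.3.6 would defer the same treatment.

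The stake is therefore patient safety and consistent conduct across up to 20 centers. The point does not bear on sample size, error rates or the two-stage decision rule.

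**Working it through.** **Comparing the rules.** No figure in the plan needs reproducing on the main question. The two texts can be compared case by case for palliative radiation to a non-target lesion.

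| Situation | Criterion 20 | Section 9.3.3.6 | Agree? |
|---|---|---|---|
| Urgent or emergent need, during doxorubicin | Allowed | Not advised against | Yes |
| Non-urgent need, during doxorubicin | Allowed | Advised against | No |
| Non-urgent need, doxorubicin finished | Allowed | Advised against if read literally; the stated reason is doxorubicin | Unclear |

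The second row is the finding. The third row arises because the sentence in Section 9.3.3.6 has no time limit. Its heading and both reasons concern doxorubicin, so the finding is confined to the doxorubicin cycles. The open wording does matter for the fix.

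**Looking for text that reconciles them.**
- Section 8.7 (concomitant medications) and its subsections contain no radiotherapy rule. The allowance for supportive care under institutional guidelines does not narrow criterion 20.
- Exclusion criterion 21 concerns earlier radiation to the mediastinal or pericardial region. It does not govern radiation given on study.
- The Schedule of Assessments and the SAP do not say which text prevails.
- Neither criterion 20 nor Section 9.3.3.6 cites the other.

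**Length of the period.** Inputs: six cycles and 18 weeks (Section 5.1), 21-day cycles with doxorubicin on Day 1 (Section 5.2.2).
- Planned doxorubicin phase: 6 x 21 = 126 days; 126 / 7 = 18 weeks, matching the protocol's figure.
- First to last planned dose: (6 - 1) x 21 = 105 days. This is the planned window in which a further doxorubicin dose can still follow on-study radiation, so it is the relevant one for recall.

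Holds lengthen the phase. Section 9.3.1 does not say when its 42 days start, so two assumptions are shown for one full hold:
- Counted from the last dose: the next Day 1 slips by 42 - 21 = 21 days, giving 126 + 21 = 147 days (21 weeks).
- Counted from the missed Day 1: 126 + 42 = 168 days (24 weeks).

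Neither is an upper limit, because longer holds can be approved. The phase is shorter if doxorubicin stops early.

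**The case against.** The strongest reply is that these are a general permission and a specific caution, not rival rules. Criterion 20 limits radiation by lesion type, which fits a wish to protect target-lesion assessment, and is silent on timing. Section 9.3.3.6 deals specifically with radiation and doxorubicin. A site that follows it breaches nothing in criterion 20. The hazard has its own heading, Sections 3.7.2 and 5.2.2 send investigators to the doxorubicin package insert, and Section 13.8 provides regular safety calls. On this view only a cross-reference is missing.

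Much of that stands. The wording of Section 9.3.3.6 is advisory, and reading it as a limit on the permission is sensible. But the protocol never states that reading, and a permission in the eligibility criteria that runs against the protocol's own safety advice can lead a site to the wrong action.

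A second reply is that criterion 20 already accepts elective radiation finished two weeks before the first doxorubicin dose, so some recall exposure is tolerated by design. That is fair, and it weakens the recall argument. It does not answer sensitization, and the on-study clause sets no interval at all before the next dose.

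A reader might infer more than the documents support:
- *That sites cannot comply with both texts.* They can, by not using the permission for non-urgent cases during doxorubicin.
- *That the permission is empty.* It remains usable for urgent palliation throughout and, if Section 9.3.3.6 is tied to doxorubicin, for elective palliation afterwards.
- *That 126 to 168 days measures risk.* It measures treatment length. The documents give no rate of on-study radiation.

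**Conclusion.** The inconsistency is real and narrow. For non-urgent palliative radiation to a non-target lesion while doxorubicin is being given, criterion 20 permits what Section 9.3.3.6 advises against, and nothing says which governs. It should be corrected, because the result may be avoidable exposure to a toxicity that the protocol itself identifies.

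The planned period is 18 weeks per patient, or 105 days from first to last planned dose where recall is the concern. How many patients would be irradiated cannot be derived from the documents.

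The conclusion rests on one assumption: that the advice in Section 9.3.3.6 is meant for the doxorubicin phase, inferred from its heading and reasons. If it were meant for the whole study, the disagreement would extend into monotherapy.

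**What to change.** Make two linked edits.

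1. In criterion 20, in both the Synopsis and Section 6.2, keep "palliative radiation to non-target lesions while on study is allowed" and add: during the doxorubicin cycles, radiation should be given only for urgent or emergent need (see Section 9.3.3.6). Do not restrict the permission to non-target lesions only, so that urgent radiation to any lesion remains possible.
2. In Section 9.3.3.6, begin the last sentence with: While receiving doxorubicin (Cycles 1-6). End it with: see inclusion criterion 20 for palliative radiation to non-target lesions.

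The second edit is needed. If only criterion 20 were changed, Section 9.3.3.6 would still have no time limit, and read literally the same disagreement would persist from Cycle 7 onward.

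The cost is one clause in two places and one revised sentence. Elective palliation is deferred while doxorubicin is given: 18 weeks as planned, longer if doses are held. Section 9.3.3.6 already advises this.
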